# STUDY SYNOPSIS

Sponsor / Sponsor- Investigator	Bernafon AG	
Study Title:	A comparative, controlled, clinical investigation of a currently marketed hearing aid programmed with two different fitting methods.	
Short Title / Study ID:	BF002-1707	
Protocol Version and Date:	Version 3.0; 2017.12.21	
Trial regist ration:	SNCTP, clincialtrials.gov	
Study category and Ration ale	Category C: Medical Device without CE mark	
Clinical Phase:	Pre-market validation study involving human subjects.	
	This clinical investigation is designed to evaluate different methods of fitting a currently marketed hearing instrument system. As human subjects are involved, this validation test falls under the definition of a clinical investigation. The validation addresses the subjective benefit of the instrument when fit with different approaches. Does the end user perceive a difference between the fittings? Evaluating the overall safety is important for pre-market performance and safety validation.	
Back ground and Ration ale:	Benefits of amplification and accessories used with it outweigh anticipated risks in mild to profound hearing-impaired subjects. The basic benefit of amplification should be present with any method that the trained professional fitting the instruments uses. The goal of this study is to compare two fitting methods and determine whether the end user perceives more benefit from one fitting method over the other. The objective benefit is expected to be the same; however, the subjective benefit may be different due to a possible psychological effect from more effort or time spent by the trained professional.	
	Bernafon will conduct this clinical investigation to test current hearing instruments fitted with the standard procedure and a self-directed procedure. Safety and performance validation of the new self-directed fitting software is needed before release to the market.	
	The reason for this study is to evaluate a currently marketed, CE certified, hearing aid and determine whether different fitting methods provide the same perceived benefit. Additionally, this study will validate the safety of the fitting procedure as well as collect post market safety information about the devices themselves. The goal is to evaluate the audiological performance objectively as well as the subjective benefit. Furthermore, it is important to identify unexpected, unwanted behavior from the fitting software and the devices.	
Objective(s):	The purpose of this research is to determine the potential of a narrative influence on the subjective benefit of the hearing instruments with the traditional fitting method versus the self-directed method. Furthermore, the objective benefit of the hearing instruments should not be affected by using a different fitting method. The gain applied by each fitting method should be the same and will be controlled by electro-acoustical measures.	

Outcom e(s):	Primary Endpoint:			
	
 
Primary Outcome is the subjective benefit with the standard fitting compared to the self-directed fitting (using questionnaires)
 
			
	Secondary Endpoints:			
	
 
Audiometry will be compared using the standard measurement made by the Investigator as a control against the self-directed measurement
 
			
	Comparison of the objective performance of the devices (using speech testing)			
	
 
Procedural safety meaning that there are no unwanted noises or artefacts heard from the devices (as reported by the subjects)
 
			
	
 
Scores from speech tests and questionnaires will be compared between the self-directed fitting and the standard fitting method.
 
			
	
 
No unexpected, unwanted behavior of the devices or unexpected device related AEs or SAEs.
 
			
Study design :	This is a controlled, randomized, cross-over, open label, comparative clinical investigation conducted at two sites within the canton of Bern.			
	The study is based on a population of hearing impaired people that have hearing loss appropriate for the tested devices.			
	The treatment assignment of participants is randomized as well as the test condition order during the lab testing.			
	The standard fitting method will be used as a control. The hearing instruments will be exactly the same.			
	There is no placebo or "fake" device that does not provide amplification. A randomized cross-over design is used with half of the test subjects wearing the device fit with the traditional fitting method first and the other half using the self-directed method and then switching after approximately $10 + -5$ days.			
	A lab test will be used to test speech in a simulated environment. After each field trial period, the participants will be tested unaided and aided with speech material.			

Inclusion / Exclusion	Inclusion Criteria:
criteria:	All types of hearing loss (sensorineural, conductive, mixed)
	
 
If the hearing loss is conductive or mixed it must first be approved for amplification by a physician
 

	All shapes of hearing loss (flat, sloping, reverse slope, notch)
	

Severity ranging from mild to severe

First time hearing aid users (never worn hearing aids before)

	German speaking
	Both genders
	
 
Ages 18 and older
 
Ability and willingness to sign the consent form
 

	Exclusion Criteria:
	Current hearing aids users
	
 
Contraindications for amplification
 
Active ear disease
 

	
 
Inability to follow the procedures of the study due to language problems, psychological disorders, dementia, or other cognitive
 

	
 
problems of the participant
 
A reduced mobility unable to attend weekly study appointments
 
A reduced ability to describe auditory impressions and the usage of the hearing aids
 

	
 
Uncooperative so that it is not possible to record a valid pure tone audiogram
 

	

A strongly reduced dexterity

With psychological problems

	
 
With psychological problems
 
Central hearing disorders
 

	

Bernafon employees

Family members of Bernafon employees

Measurements and procedures:	A hearing test will be made using standard audiometry performed by the investigator and a hearing screening using the new self-directed software which includes an automated screening. Amplification is fitted either using the first fit procedure with the standard Oasis software (RMD) or with the new self-directed software (IMD) that uses a simplified version of the existing Oasis software. First fit in the context of this trial will mean without any additional fine tuning. During a normal first fit it is possible to make changes based on subject comments. However, to maintain that the acoustic fitting of the two sets of hearing aids is the same there will be no fine tuning performed.
	The subjects will complete a standardized questionnaire that measures their perceived handicap of the hearing loss (Gothenburg). Two additional questionnaires will be used to measure a possible narrative effect on the subjective perception of the fitting procedures. A standardized questionnaire, IOI-HA, and a custom product questionnaire will be used after each 10-day field test to evaluate the benefit of amplification with the RMD and the IMD. Also, a custom packaging questionnaire will be used after each fitting to measure the usability of the packaging of the RMD and the IMD. At the last appointment the participants will complete a preference questionnaire. Speech intelligibility tested in quiet will be measured with both fittings. The
	speech material will be a multi-syllable word test called the Freiburger Wörttest (FST) with the speech presented from a speaker in front of the subject.
	Safety is measured by reported unexpected sounds from the hearing aids verbally. Safety is also measured by AEs or SAEs reported at visits.

Study Product /	HearToo Software
Intervention :	The new self-directed fitting software is not CE marked. It is a combination of two entities: a self-directed hearing screening based on a known algorithm from Audiology Inc. sold in an automated audiogram by Grason Stadler, GSI (Eden Prairie, MN) and a simplified version of the Oasis software. The flow of the new software is driven by the end user, but a trained professional should always assist with the fitting. The new software will first perform a hearing screening on the end user and then recommend a hearing aid and prescribe amplification to the hearing aid based on the hearing screening results. Please see the IB for a full description of the self-directed fitting device. An additional medical device used for the trial is the Juna 7 behind-the-ear (BTE) hearing device. It was released to the market in 2015.
Control Intervention (if applic able):	The reference intervention is the standard accepted method of fitting hearing instruments. The software version used to program the Juna 7 devices with the traditional fitting is CE marked and has been used on the market since the release of the Juna product in 2015. The performance and subjective benefit of a self-directed fitting method will be tested against the standard. For the purposes of this trial the standard fitting method will be referred to as the RMD and the new self-directed fitting software will be the IMD.
Number of Participants with Rationale:	There will be an exploratory analysis of data only. The total number of participants will be a minimum of 24 (no more than 40), and the explanation for this sample size is as follows:
	A literature search about this tested topic does not provide enough strong references to build a confirmatory analysis. It seems that results might be strongly influenced by the inclusion criteria (first time vs experienced hearing aid users) or test design (cross-over, multi-investigator, or between group designs). There is no article to our knowledge that includes a multi-investigator effect in the test design when looking at the effect of different fitting procedures. Adding a treatment interaction term seems to be mandatory if this trial wants to determine the effect that different investigators may have. Each investigator shall treat the same amount of subjects.
	The 24-40 subjects will participate in 2 field studies, but randomized into different fitting/intervention groups with half the number of subjects in each group.
Study Duration:	Approximately 3 months
	The screening of the participants will begin in February of 2018 and the final data collection appointments will occur in April 2018.
Study Sched ule:	The first participant is expected to begin in February 2018.
	The last participant is expected to finish the testing in April 2018.
Investigator(s):	[name], Research Audiologist, Doctor of Audiology
	[name]
	[contact] [contact]
Study Centre(s):	The testing will be performed at two clinical sites in canton Bern, Switzerland.
Statist ical Consider ations:	The analysis and documentation will be performed by the statistician using the latest validated R version with R Studio as IDE. Appropriate data analysis will be performed with parametric and non-parametric tests on questionnaire outcomes, hearing threshold measures, and speech test scores.

GCP Statement:	This study will be conducted in compliance with the protocol, the current version of the Declaration of Helsinki, the ICH-GCP or ISO EN 14155 (as far as applicable) as well as all national legal and regulatory requirements.
	Tal as applicable) as well as all flational legal and regulatory requirements.

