#### 4.2 Primary Objective

The study seeks primarily to determine if the subjective benefit of the hearing aids fitted with the IMD is as good as the RMD. Does one fitting method provide a psychological effect that influences the participants? As a second primary objective the study seeks to proactively determine if there is any unknown and/or unwanted behavior from the IMD. The study seeks to validate that the performance of the IMD is not inferior to the RMD.

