#### 4.4 Safety Objectives

The study aims to validate the overall implementation of the IMD. The study will test for unexpected behavior from the IMD and new risk factors to ensure safety of the devices before they are released to the market.

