### 11.2 Determination of Sample Size

A literature search about this tested topic does not provide enough strong references to build a confirmatory analysis. It seems that results might be strongly influenced by the inclusion criteria (first time vs experienced hearing aid users) or test design (cross-over, multi-investigator, or between group designs). There is no article to our knowledge that includes a multi-investigator effect in the test design when looking at the effect of different fitting procedures. Adding a -by investigator- treatment interaction term seems to be mandatory if this trial wants to be determine the effect that different investigators have on the fitting procedure.

The sample size cannot be computed on reported effect sizes from previous experiment; however, the following summary shall be used as an indication to determine the sample size for participants per investigator:

•Naylor et al. (2015) about the narrative effect during the fitting with 24 experienced users and 16 first time users,

•Humes et al. (2017) about the performance with over-the-counter hearing aids compared to audiology best practice with 154 participants,

•Dawes et al. (2013) about the placebo effect in hearing aid trials with 16 experienced hearing aid users,

•Dawes et al. (2011) about the placebo effect in hearing aid trials with 20 experienced hearing aid users.

A placebo effect was found with sample sizes of about 20 participants in a single site study design. Adding an investigator effect in the design might bring new insights in this domain but requires a minimum number of participants per investigator to reduce imbalance between them.

With an effect size of 0.65 from the literature review, 2 degrees of freedom, 24 participants, and an alpha of 0.05, we can achieve a power of 0.82. Therefore, a minimum of 24 participants will be included in the trial overall. There will be 4 investigators with 6 to 8 participants per investigator.

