#### 11.4.6 Safety analysis

Safety analysis is foreseen to be accomplished with the AEs reported by the participants during the trial. Clinical judgement from the PI will be used for the safety evaluation.

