3.2 Power analysis

The expected power as a function of the effect size can be computed with G*Power (version 3.1.9.2).

Preference: χ^2 distribution can be used to investigate if the preference distribution is due to chance or to the manipulated effect. We can compute the effect size from the reported literature with Cohen's w (Cohen, 1988):

$$W = \sqrt{\frac{(p_{0i} - p_{1i})^2}{p_{0i}}}$$

where p_{0i} is the value of the *i*th cell under H0 and p_{1i} is the value of the *i*th cell under H1. However, there are two possible analysis options that can be differentiated by the counting method.

1. with 2 outcomes i.e. there is an audible difference or not,

Naylor (2015) experiment 1: w = 0.67Naylor (2015) experiment 2: w = 0.75Naylor (2015) experiments 1 and 2: w = 0.7Dawes (2011) experiment 1: w = 0.5Dawes (2013) experiment 2: w = 0.5Dawes experiments 1 and 2: w = 0.5All the experiments together: w = 0.6

With an effect size of 0.6, 1 degree of freedom, 24 participants and α of 0.05, we can achieve a power of 0.84. This analysis method is used by Dawes in his papers because only one device was preferred over the other if the listeners had a preference. The influence of effect size variation on the achieved power is show in figure 1.

This analysis allows to answer the question is there is a difference between both method used in the test. But it does not give an indication about the preferred method.

2. with 3 outcomes i.e. preference for A, preference for B, or no preference,

Naylor (2015) experiment 1: w = 0.54Naylor (2015) experiment 2: w = 0.47Naylor (2015) experiments 1 and 2: w = 0.5Dawes (2011) experiment 1: w = 0.94Dawes (2013) experiment 2: w = 0.94Dawes experiments 1 and 2: w = 0.94all the experiments together: w = 0.65

With an effect size of 0.65, 2 degrees of freedom, 24 participants and α of 0.05, we can achieve a power of 0.82. The influence of effect size variation on the achieved power is show in figure 2.

Adding a degree of freedom in the analysis leads to a small loss of power, even if it is always higher than 80%. However, it might give more information about which method will be preferred.

[figure not shown]

Figure 1: Expected power as a function of the effect size with analysis on 2 levels (audible difference or not)

[figure not shown]

Figure 2: Expected power as a function of the effect size with analysis on 3 levels (preference for A, preference for B or no preference)

4. Analysis

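### With 24 to 40 participants, a safety result of no events supports signal detection, not a statement that safety is ensured, and the plan gives no rate or limit to go with it

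*Protocol*

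**What the plan says.** **Endpoints.** The protocol synopsis (Outcome(s)) lists among the secondary endpoints: "Procedural safety meaning that there are no unwanted noises or artefacts heard from the devices". A separate item there is the absence of unexpected device behaviour and of unexpected device-related AEs or SAEs. Protocol 4.2 ranks part of this higher: "As a second primary objective the study seeks to proactively determine if there is any unknown and/or unwanted behavior from the IMD".

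**Purpose.** Protocol 4.4 says the testing is "to ensure safety of the devices before they are released to the market". The synopsis background says the study will validate the safety of the fitting procedure, and section 13 gives the main use of the results as product validation for safety and performance. Sections 5.4 and 9.2.4 are more modest: the field data are to alert the sponsor or testers to possible risks.

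**Analysis.** Protocol 11.4.6 uses the AEs that participants report and adds: "Clinical judgement from the PI will be used for the safety evaluation". The SAP has no safety analysis. Neither document gives a tolerable event rate, a confidence limit or a decision rule for safety.

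**Size.** The synopsis and section 7.3 plan 24 to 40 participants. Section 11.2 gives a narrower range: "There will be 4 investigators with 6 to 8 participants per investigator", that is 4 × 6 = 24 to 4 × 8 = 32. Each participant is fitted once with each method (section 3.1).

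**Expected result.** Section 9.2.4 does not expect any of the listed events to occur.

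**The concern.** The sponsor's own expectation is an empty list of events, so the plan should say what an empty list would mean. It does not. A count of zero in a small sample excludes only fairly common events, yet the objectives speak of validating and ensuring safety before market release. With no denominator or upper limit reported, the reader of the final report cannot see how far the result reaches.

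At stake are an objective that section 4.2 calls primary and the safety statement that goes forward to the release decision. The risk is an overstated conclusion. Nothing here suggests that the device is unsafe.

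**Working it through.** **1. What the sample size was built for.** The only power figures in the documents concern the preference question. SAP 3.2: "With an effect size of 0.65, 2 degrees of freedom, 24 participants and α of 0.05, we can achieve a power of 0.82". Check: noncentrality = N × w² = 24 × 0.65² = 10.14; the 5% critical value of chi-square on 2 df is 5.99; power = 0.821. The stated 0.82 is reproduced. The two-outcome version (w = 0.6, 1 df) gives 0.836 against the stated 0.84. Neither figure bears on safety.

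**2. What zero events excludes.** Let p be the true proportion of users with a given event and n the number exposed. The chance of seeing none is (1 − p)^n. Setting this equal to a and solving gives the exact upper limit p = 1 − a^(1/n), with a = 0.05 for a one-sided 95% limit and a = 0.025 for the upper end of a two-sided 95% interval.

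| n | Source of n | One-sided 95% | Two-sided 95% |
|---|---|---|---|
| 24 | planned minimum | 1 − 0.05^(1/24) = 11.7% | 1 − 0.025^(1/24) = 14.2% |
| 32 | top of the range in 11.2 | 8.9% | 10.9% |
| 40 | planned maximum | 7.2% | 8.8% |

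If only 20 participants were counted (an assumption, since the documents give no dropout rate), the limits would be 13.9% and 16.8%.

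**3. Chance that an event is missed altogether, (1 − p)^n.** The true rates are illustrations, because the documents give none.

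| True rate | n = 24 | n = 32 | n = 40 |
|---|---|---|---|
| 1% | 79% | 72% | 67% |
| 2% | 62% | 52% | 45% |
| 5% | 29% | 19% | 13% |
| 10% | 8% | 3% | 1.5% |

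So the trial is a reasonable detector of events that affect about one user in ten, and a weak one for events that affect one in fifty.

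**4. Size needed to exclude a given rate with zero events.** For an upper limit below 10%: 29 participants (one-sided) or 36 (two-sided). Below 5%: 59 or 72. Below 1%: 299 or 368. These too are illustrations.

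**5. The denominator.** The documents disagree on whose data count:
- Protocol 7.4 and 8.3: data from participants who withdraw or discontinue are used.
- Protocol 8.5: withdrawn participants' data enter no final analysis or report.
- Protocol 10.1: a participant whose pain prevents use of the device is withdrawn, partly so that incomplete data are removed.
- Protocol 11.5: complete cases only. Sections 11.3 and 11.4.1 describe a per-protocol analysis.

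If one of 24 exposed participants had an event and was then dropped, the count would change from 1/24 to 0/23. The exact two-sided upper limit for 1/24 is 21.1%, the p at which (1 − p)^24 + 24p(1 − p)^23 = 0.025. For 0/23 it is 1 − 0.025^(1/23) = 14.8%. The exclusion would erase the signal and also lower the limit.

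**The case against.** The strongest reply is that the plan makes no inferential safety claim. The synopsis announces exploratory analysis only, and section 6.1 calls the study exploratory. Sections 5.4 and 9.2.4 describe signal detection. Section 4.4 states an aim, not a conclusion. Collection is broader than the noise endpoint: section 10.1 provides for AEs to be collected at every visit and for a participant diary. Other evidence exists too: a completed software test (3.3), a risk analysis (3.7), a capped test output (8.1.1) and hearing aids already on the market (3.1, 3.2). The arithmetic of zero events applies to any small study, and the listed events run from whistling and occlusion to shut-off during use, so a limit of 7% to 14% will not matter equally for all of them.

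Much of this stands. A reader might infer that the protocol treats zero events as a formal pass for safety and that the design fails its own test. The documents do not support that: they set no such rule and no tolerable rate. A reader might also take 12% to 14% as the figure for the trial, but it belongs to the minimum of 24; the planned range gives about 7% to 14%.

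What the reply does not remove is the wording. If the purpose is signal detection, the synopsis background and sections 4.4 and 13 claim more than that. The bench and risk evidence may support release, but it does not make a zero in this trial more informative. And because the events are not ranked by seriousness, each needs its own count and limit.

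**Conclusion.** The concern holds as a mismatch between the safety wording and the safety analysis. No stated threshold is missed. Across the planned 24 to 40 participants, a zero-event result leaves per-participant rates of up to about 7% to 12% (one-sided 95%) or 9% to 14% (two-sided 95%) possible. It can be reported as no signal seen, with that limit, but not as safety ensured or validated.

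The figures assume that every enrolled participant is exposed to the IMD and counted, that participants are independent, and that every event is reported. Loss of participants from the count, clustering by investigator or under-reporting would all make a zero less informative. The contradiction over withdrawn participants' data makes the first assumption uncertain.

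This is worth correcting before the analysis. It does not call for a larger trial.

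**What to change.** 1. **Protocol 11.4.6, and a matching line in the SAP.** For each event listed in 5.4 and 9.2.4, and for device-related AEs and SAEs, report participants affected over all participants exposed to the IMD, including those later withdrawn. Give a two-sided exact (Clopper-Pearson) 95% interval at the achieved number. Keep the principal investigator's judgement alongside it.
2. **Define exposure.** Everyone takes the IMD hearing screening at visit 1, but half are fitted with the IMD only at visit 2 (study schedule footnote). State which denominator applies to events during screening and which to events in the IMD field period.
3. **Wording.** In the synopsis (background and outcomes) and in sections 4.4 and 13, replace the language of ensuring or validating safety with a descriptive aim. Have a zero-event result read: no event seen; upper limit of the two-sided 95% interval X%, with X computed from the achieved number and not fixed in advance.
4. **Reconcile sections 7.4, 8.3, 8.5, 10.1 and 11.5** on the use of withdrawn participants' data, so that an exposed participant with an event is not lost from the safety count. This concerns the data only, not when a participant should stop using the device.

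The cost is a short table, some redrafting and a less favourable safety statement. No extra participants or visits are needed.
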